15.2 Power Analysis: For the power analysis for the primary analyses, we calculated the minimum detectable effect size (MDES) assuming $n = 200$, a $\alpha = .05$, and power = .80 with 12 covariates in our model. Power was estimated in R (R Core Team) using the pwr library (Champely, 2018). A power analysis was performed to quantify the minimum detectable effect size (f^2) for a three-way interaction between social buffering condition, sex, and pubertal stage within a multiple regression model controlling for the 12 covariates, all two-way interactions, and the main effects (the most complex model considered in our primary analysis, see Equation 1 below). Assuming these conditions, we should be able to detect an f^2 of 0.056. In other words, adding the three-way interaction to a model containing the covariates and all lower order interactions and main effects, the three-way interaction would need to explain an additional 5.6% of the variability to be detected. This falls between Cohen's criteria for a small ($f^2 = .02$) and medium effect ($f^2 = .15$) (Cohen, 1988). With a sample size of 200, even if we lose 40 of the participants to movement artifact for the imaging analyses, assuming all the previous conditions but a sample size of 160, we will still have an f^2 of .070, or still within a small-medium effect size. As the number of covariates decreases, the size of the MDES will decrease. Therefore, this represents a conservative estimate of the power for our primary analyses as we are likely to have fewer covariates in our models

and will use multiple imputation to correct for missing data. For the two-way interaction and main effects models, described below, the power will be larger than these reported values as the models will be simpler.

15.3 Statistical Analysis of MRI and non-MRI Outcome Variables:

The following is a list of the analyses that we will perform on the outcome measures. They are classified as to whether they are the primary or mediational analyses. All statistical analyses will be performed in R.

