The primary analyses will consist of a series of multiple regression models. For each dependent variable, variation in neural activity, cortisol, and physiological responses, we will begin by testing the three-way interaction between social buffering condition, sex, and pubertal stage for all outcomes. If the three-way interaction is not significant, we will then examine all two-way interactions. If the two-way interactions are not significant, we will then examine main effects only models. If the three-way interaction is significant, we will not examine any other model. If condition is significant as an interaction or as a main effect, we will examine all pairwise comparisons using Tukey's Honestly Significant Difference test.

Multiplicity of testing. We will correct for multiple comparisons using the Benjamini-Hochberg (BH) correction. The BH method works by controlling the false discovery rate, and relative to the Bonferroni's correction is more powerful, while still adequately protecting against Type I error (Williams, Jones, & Tukey, 1999).

Mediational Analysis. When changes in activity of brain regions differ by condition or condition by pubertal status and we also see condition or condition by pubertal status differences for cortisol or physiological measures, then we will examine whether brain activity differences mediate the neuroendocrine or physiological differences. This will be examined using path analysis, while controlling for covariates identified in the preliminary covariate analysis, and will be estimated using the lavaan package in R (Rosseel, 2012).

The significance of all indirect effects will be assessed using bias-corrected 95% confidence intervals (Efron & Tibshirani, 1986), where confidence intervals that are non-overlapping with zero will be considered significant.

Power Analysis for the Mediational Analysis: To assess power to detect mediation, we performed a Monte Carlo-based power analysis using simulated data. We varied the parameter values to roughly correspond to Cohen's criteria for small, medium, and large effects. This resulted in a total of 27 conditions, which we examined at our target sample size of 200. Each

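### Under the Section 15.3 testing sequence, a significant sex × pubertal stage term, which does not involve condition, can leave an outcome with no condition comparison

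*Combined protocol and SAP*

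**What the plan says.** Section 15.3 sets one sequence for every dependent variable. The three-way interaction of condition, sex and pubertal stage comes first. If it is significant, modelling ends: "If the three-way interaction is significant, we will not examine any other model". If not: "If the three-way interaction is not significant, we will then examine all two-way interactions". The last step is conditional on the second: "If the two-way interactions are not significant, we will then examine main effects only models". Follow-up is conditional too: "If condition is significant as an interaction or as a main effect, we will examine all pairwise comparisons", by Tukey's method. The mediation analysis has its own trigger: "When changes in activity of brain regions differ by condition or condition by pubertal status", together with a matching difference in cortisol or physiology.

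Elsewhere, Section 4.1 gives the reason for randomising as learning what the social partner does to the stress response. Section 5.1 says that outcomes will be compared between the three conditions. Hypotheses 1 and 2 (Section 2.3) concern the parent and friend effects and their change with puberty, and do not mention sex. Section 3.2 lists sex differences across conditions by puberty as a secondary exploration, whereas Section 15.2 calls the three-way model "the most complex model considered in our primary analysis".

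**The concern.** There are three two-way interactions: condition × sex, condition × pubertal stage and sex × pubertal stage. The first two contain condition. If either is significant, there is good reason not to report a single condition effect, and the Tukey rule applies. The third does not contain condition. It says only that the puberty slope differs between boys and girls, which gives no reason to withhold a comparison of randomised groups. Yet nothing in Section 15.3 exempts it from the gate.

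Suppose that sex × pubertal stage is the only significant term. Read literally, the main-effects model is then not fitted, condition has not been significant in any form, Tukey is not triggered, and the outcome ends with no condition comparison. A parent or friend effect on that outcome could go unreported because of a feature of development unrelated to the randomisation. The mediation step for Hypothesis 3 would lose its trigger as well. The plan also leaves open whether any one term or a joint test closes the gate, and whether significance is judged before or after the Benjamini-Hochberg (BH) correction.

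**Working it through.** **1. The plan's own figure.** Section 15.2 gives n = 200, alpha .05, power .80 and 12 covariates, and states "we should be able to detect an f^2 of 0.056" for the three-way term. With three conditions and linear pubertal stage there are 12 + 4 main-effect + 5 two-way + 2 three-way = 23 predictors, so u = 2 and v = 200 − 24 = 176. With λ = f²(u + v + 1), 80% power needs f² = .0548. At .056, λ = .056 × 179 = 10.0 and power is 80.9%. At n = 160, v = 136 and f² = .0709, against the stated .070. The figure reproduces. At the 150 children of Section 5.1, v = 126 and f² = .0765.

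**2. How often the gate closes with no true interaction** (each test at unadjusted .05, treated as independent).
- Any one of three two-way terms closes it: main effects reached in .95 × .95³ = .81; simulated about .82. Of the 18% not reached, about 5 points come from the three-way term, 9 from a two-way term with condition and 4 from sex × puberty alone (n = 150, no covariates).
- A joint 5-df test closes it: .95 × .95 = .90; simulated .90.

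**3. Assumed effects.** The documents give no expected effects, so Section 15.2's benchmarks are used.
- Condition: parent effect 0.5 SD in one of three equal arms; f² = .5² × (1/3)(2/3) = .056.
- Sex × puberty: slope difference b per SD of puberty, sexes 1:1, sex–puberty correlation .3; f² = (b²/4)(1 − .09). b = .3 gives .020 and b = .5 gives .057, close to 15.2's small effect (.02) and its detectable effect (.056). These values are assumptions, not predictions.

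**4. Closed-form check, n = 200, 12 covariates.**
- Direct condition test: u = 2, v = 183, power .82.
- Sex × puberty test: u = 1, v = 178, rejection .05 / .47 / .88 at f² = 0 / .02 / .056. Any-one gate: .82 × .95³ × (1 − rejection) = .67 / .37 / .08.
- Joint 5-df test: rejection .05 / .26 / .68. Joint gate: .82 × .95 × (1 − rejection) = .74 / .58 / .25.

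**5. Simulation** (12 covariates, unadjusted .05; approximate, repeated runs agree within about 3 points). Condition main effect found, at sex × puberty f² = 0 / .02 / .056:

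| | n = 200 | n = 150 |
|---|---|---|
| Direct test | about 80% (79–83%) | 64–70% |
| Literal sequence, any one term | 67 / 38 / 8% | 55 / 37 / 14% |
| Literal sequence, joint gate | 75 / 58 / 25% | 61 / 51 / 30% |

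If only interactions containing condition can close the gate, the n = 200 figure is 69–71% throughout. Changing the sex–puberty correlation to 0 moves the sequence figures by less than 2 points.

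**6. Whether any condition term is found, n = 200.** Under the same assumptions and the literal sequence: 81 / 53 / 22% (any one) or 83 / 70 / 39% (joint). With no sex × puberty effect, then, the loss is mostly relabelling.

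**7. The three-way stop.** For a true condition × puberty slope of .5 (n = 150, no covariates), power is 65.4% in the two-way model without the stop and 62.3% through the sequence, a cost of about 3 points.

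**The case against.** The strongest reply is that the explicit stop attaches only to the three-way term. No such words follow the two-way step, and the Tukey sentence speaks of condition being significant as an interaction or as a main effect. A retained two-way model would normally contain the condition main effect, so an analyst could read it there. With centred terms at n = 200 that finds condition in about 77–79%, a loss of only 2–4 points against the direct test. This stands as a reasonable reading, but the plan does not state it.

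Second, the simulated truth has a constant parent effect, while the central hypothesis is that buffering wanes with puberty. With a waning slope of −.5 added at n = 200, some condition term is found in about 89–96% at slope differences of .3 and 0, even under the any-one gate. At n = 150 it is 79% and 87%. This stands too: condition × puberty is always tested once the three-way term is not significant.

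Third, the lowest figures need a sex × puberty effect as large as the plan's detectable effect for another term, and gates at unadjusted .05. A stricter .01 gate, for illustration, raises the any-one figure at b = .3 and n = 200 from 36% to 60%.

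Two stronger readings are tempting. A reader might infer that the three-way stop is itself the main harm; not interpreting lower-order terms under a significant higher-order one is ordinary practice, and the cost in step 7 is small. A reader might also infer that Section 15.2 is wrong to say "For the two-way interaction and main effects models, described below, the power will be larger than these reported values"; that sentence concerns the models as fitted, not the chance of reaching them.

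**Conclusion.** The defect is real but conditional. As worded, Section 15.3 lets a term without condition decide whether the condition main effect is tested. That sits badly with the purpose in Section 4.1 and the comparison in Section 5.1. The documents do not support saying that the condition effect is always withheld: it is withheld only on the literal reading, when sex × puberty closes the gate and no condition term is significant.

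On that reading, the n = 200 loss for a constant 0.5 SD parent effect runs from about 13 points (80% to 67%) with no sex × puberty effect to about 72 points (80% to 8%) at f² = .056 under the any-one gate, or from about 5 to 55 points under the joint gate. On the alternative reading it is 2–4 points. A gap that wide between two readings of one sentence is enough reason to settle the wording before analysis.

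Separately, Section 3.2 treats the sex question as secondary exploration while Sections 15.2 and 15.3 make it the first primary test. Because Section 15.1 lists sex as an independent variable beside condition and pubertal stage, this is an inconsistency of status to reconcile, not evidence that sex does not belong in the model.

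**What to change.** The minimum is to state in Section 15.3 that only interactions containing condition can close the gate to the condition main effect, and that sex × pubertal stage stays in the model as an adjustment term.

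The better change is to drop the dependence. For every primary outcome, report two tests from one prespecified model that keeps sex × pubertal stage: the 2-df condition × pubertal stage test and the 2-df condition effect at mean (centred) pubertal stage, whatever the sex terms show. In simulation the latter has 81–82% power at n = 200 and 67–68% at n = 150 under the assumptions above. Making condition × pubertal stage the single primary test is a design preference and is not needed to cure the defect.

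With either change:
- Fix the BH family in advance; under the better change it includes both tests.
- Tie the mediation trigger to the prespecified condition tests.
- Reconcile Section 3.2 with Sections 15.2 and 15.3 on the status of the three-way question.

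The cost is SAP wording and a slightly larger BH family; design and data collection do not change. Detectable f² for condition × pubertal stage in a model with 12 covariates, condition, sex, pubertal stage, condition × pubertal stage and sex × pubertal stage (12 + 2 + 1 + 1 + 2 + 1 = 19 predictors) is .0535 at n = 200 (v = 180) and .0741 at n = 150 (v = 130). For the three-way term it is .0548 and .0765.

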The **long-term goal** of our research is to enrich understanding of threat-related stress regulation and its role in human development. The **overall objective** of this project is to understand normative processes in threat-related stress regulation and their neurobiological correlates as children leave childhood and become more autonomous in adolescence. The **central hypothesis** of this project is that early adolescence is a period of time when parental buffering wanes in efficacy, leaving many youth experiencing a relative dearth of relationships that can provide powerful stress buffers.

The aim of the current study is to delineate changes in brain activation in response to social buffering by parents and friends over the pubertal transition.

Hypothesis #1: Parental social buffering will result in increased activation in brain regions associated with safety (e.g. vmPFC) and lower activation in brain regions involved in fear and pain (e.g., insula, amygdala, hypothalamus), as well as tighter coupling between the vmPFC and amygdala activity, but these relationships will wane with pubertal development.

Hypothesis #2: Friend social buffering will result in less attenuation in the same brain regions, and less mPFC-Amygdala coupling than parental buffering, but will also become less effective with pubertal development.

Hypothesis #3: Neural activity associated with social buffering will mediate the effectiveness of physiological buffering by social partners.

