4.2 Drug/Device Handling: N/A

4.3 Biosafety: N/A

4.4 Stem Cells: N/A

5.0 Procedures Involved

5.1 Study Design: The study design is cross-sectional. 150 target children (10- to 15-year-olds) will be randomly assigned to one of three conditions: (1) no social support (standard MRI scanning condition); (2) presence of a parent; or (3) presence of a close friend. Outcome measures will be compared across the three social buffering conditions. Pubertal stage will be included as a continuous variable in analyses of physiological and/or brain responses.

Two tasks will be used during the MRI scanning. Both have been shown to activate stress-related regions of the brain in past studies and have been used by our labs. The order of these two tasks will be counterbalanced.

Based on the results of piloting social buffering will EITHER be done with the presence of a buffer in person, or, displayed on screen via a live Zoom feed. All conditions will use the same modality.

Study Overview:

Visit 1: Parent and child will participate in an online video session (via Zoom) lasting approximately 2 hours. Following a detailed overview of study and consent/assent procedures, participants will be asked to complete the following measures:

Parent:

- Questionnaire regarding family income, education level, and family composition
- Parent-report questionnaire about child's general health, behavior, and development (MacArthur Health Behavior Questionnaire; HBQ)
- Parent-report MRI safety screening questionnaire about the child to rule out any contraindications for MRI scanning
- *[If the child is randomized to the parent-present buffering condition],* self-report MRI safety screening questionnaire to rule out any contraindications for sitting in the MRI area

PROTOCOL TITLE: An MRI Study of Learning and Social Support

VERSION DATE: v.10 2024.12.18

- Child life challenges question

Children/adolescents:

- Questionnaire about general health, behavior, and development (MacArthur Health Behavior Questionnaire; HBQ)
- Questionnaire about their relationships with their parents and their best friend (Network of Relationships Questionnaire)
- Questionnaire about anxiety in different contexts (State-Trait Anxiety Inventory for Children)
- Pubertal development questionnaire (Morris and Udry, 1980)
- Safety screening questionnaire to confirm safety in the MRI scanner
- Perceived stress questionnaire
- Child life challenges questionnaire

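### Section 15.3 gives Tukey's HSD as the follow-up to a condition-by-puberty interaction; read in its ordinary sense, that does not show which partner's effect wanes

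*Combined protocol and SAP*

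**What the plan says.** The follow-up rule in Section 15.3 reads: "If condition is significant as an interaction or as a main effect, we will examine all pairwise comparisons", with Tukey's HSD named as the test. The same sentence covers an interaction and a main effect.

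The models are tested from the top down. The condition by sex by puberty interaction comes first: "If the three-way interaction is not significant, we will then examine all two-way interactions", and main effects are examined only after that. At the top there is a stop rule: "If the three-way interaction is significant, we will not examine any other model".

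Section 5.1 fixes the scale of puberty: "Pubertal stage will be included as a continuous variable in analyses of physiological and/or brain responses". It also sets the design: "150 target children (10- to 15-year-olds) will be randomly assigned to one of three conditions".

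Section 2.3 states the hypotheses. Hypothesis 1 expects parental buffering of the brain response, "but these relationships will wane with pubertal development". Hypothesis 2 expects weaker buffering by friends, "but will also become less effective with pubertal development".

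No section mentions slope contrasts, simple slopes, or puberty values at which conditions would be compared. The two puberty categories in Section 8.3 serve recruitment only.

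**The concern.** With puberty continuous, a condition-by-puberty interaction means that the regression of the response on puberty has a different slope in at least one arm. The test has 2 degrees of freedom for three conditions, so it does not say which arm differs. The waning part of Hypothesis 1 is the parent slope minus the no-partner slope. The waning part of Hypothesis 2 is the friend slope minus the no-partner slope.

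Tukey's HSD in its usual sense compares group means. In the main-effect half of the rule the comparisons can only be of condition means, and nothing gives the interaction half a different target. Read so, a significant interaction is followed by a comparison of average condition differences, which the interaction has just shown to depend on puberty. A report could then move from a significant interaction plus a significant pair of means to a statement that this partner's buffering wanes, without having tested it. The waning claim is the study's central hypothesis, so the contrast that supports it should be named in advance.

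**Working it through.** **The plan's own figure.** Section 15.2 gives a minimum detectable f² of 0.056 at n = 200 and .070 at n = 160 for the three-way interaction. With three conditions that interaction has u = 2. The model has 12 covariates, 2+1+1 main effects, 2+2+1 two-way terms and 2 three-way terms, 23 in all, so v = n - 24. Using λ = f²(u + v + 1) at α = .05 and power .80, I get 0.0548 at n = 200 and 0.0709 at n = 160. The figures reproduce, but they concern the omnibus test and say nothing about the follow-up.

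**Simulation inputs.** From the documents: three conditions, 150 completed participants (Sections 5.1 and 15.3), continuous puberty, α = .05. Assumed, because the documents give no effect sizes: 50 per arm, residual SD 1, puberty uniform with SD 1 (range ±√3 = ±1.73), and the effects in the table. The model has arm means, arm-specific puberty slopes and sex: 7 parameters, 143 residual df. The 2-df slope-equality F test is run at .05. Among significant runs, the Tukey critical value 2.37 is applied either to condition differences at average puberty or to slope differences.

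**Size of the interaction.** An effect that changes by d across the range has slope s = d/3.46. If only the parent slope differs, the arm slopes are (0, s, 0), their variance is 2s²/9, and f² = 2s²/9. For d = 1.0, s = 0.289 and f² = 0.0185. Then λ = 0.0185 × 150 = 2.8, which gives a power of about 0.29, in line with the simulated 28%.

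**Results, given a significant interaction** (repeated runs agree to about 2 points; effects are differences from no partner):

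| Parent effect, early to late | Friend effect | Means: parent-none | Slopes: parent-none | Means: friend-none | Slopes: friend-none |
|---|---|---|---|---|---|
| -1.0 to 0 | constant -0.5 | 56% | 59% | 54% | 6% |
| -1.0 to 0 | none | 56% | 58% | | |
| -1.2 to 0 | none | 74% | 63% | | |
| -1.8 to 0 | none | 98% | 77% | 2% | 2% |
| -0.9 to +0.9 | none | 2% | 76% | | |

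In the first row the parent-friend pair is flagged in 2% by means and 56% by slopes.

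**Why the means behave this way.** A difference of two arm means has standard error √(1/50 + 1/50) = 0.20. The chance of a flag depends only on the mid-puberty difference:
- 0.5/0.20 = 2.5, and Φ(2.5 - 2.37) = 0.55
- 0.6/0.20 = 3.0, and Φ(3.0 - 2.37) = 0.74
- 0.9/0.20 = 4.5, and Φ(4.5 - 2.37) = 0.98
- 0, and 2 × (1 - Φ(2.37)) = 0.02

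These match the simulated columns. The slope does not enter. A partner whose effect wanes from -1.0 to 0 and a partner with a constant -0.5 have the same mid-puberty difference, so the means cannot tell them apart.

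**Larger sample.** At n = 201, with a parent mean of -0.52, a slope of 0.3 and no friend effect, the interaction is significant in 41% of runs; means then flag the parent in 73% and slopes in 62%.

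**The case against.** The plan does not say that HSD is applied to condition means, or at average puberty. The rule is triggered by a significant interaction within regression models fitted in R, so it could be read as Tukey-adjusted comparison of whichever condition effect was significant, slopes included. This stands: comparison of means is the ordinary reading of HSD, not the plan's explicit wording. But the slope reading is not written either, and the choice would then be made after the data are seen, across many outcomes.

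A reader might infer that the central hypothesis has no valid pairwise test. The documents do not support that. The fitted interaction model already contains the slope differences. If condition is coded against the no-partner arm, two of its coefficients are the waning contrasts of Hypotheses 1 and 2. The coding is not stated; Section 15.2 points to an equation that is not in the text available to me and might show it. What is missing is the stated, multiplicity-adjusted comparison.

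A reader might also infer from the last row of the table, 2% against 76%, that the follow-up would usually find nothing. That row needs the parent effect to reverse fully, with harm late in puberty equal to the benefit early on. Hypothesis 1 speaks of waning, and Section 2.2 reports no parental effect in older adolescents, not a reversal. When the parent effect wanes to zero and the friend has none, means flag the parent as often as slopes or more often.

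Nor do means name a wrong partner in the first row. The friend has a true mean effect there, and the flag is correct about that mean. It misleads only if it is read as evidence of waning.

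**Conclusion.** The point holds as a mismatch between the stated follow-up, in its ordinary sense, and the hypotheses it serves. Comparing condition means does not test which partner's effect changes with puberty.

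The practical size depends on the pattern. It is clearest when one partner's effect wanes and the other's is constant: means flag the two about equally, while slope contrasts separate them (59% against 6%). That figure applies only to the roughly 28% of runs in which the interaction is significant at 150 children. When only one partner has an effect and it wanes to zero, means usually point to the right partner, yet they still do not show waning.

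All of this rests on assumed effect sizes, equal arms, uniform puberty and no covariates other than sex. The omnibus interaction test is unaffected. This should be corrected before analysis; it does not undermine the design.

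**What to change.** In Section 15.3, split the follow-up rule by the model that triggered it.

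- **Main-effects model:** keep Tukey's HSD on condition means.
- **Significant condition-by-puberty interaction:** use Tukey-adjusted pairwise contrasts of the puberty slopes (parent minus none, friend minus none, friend minus parent) from the model already fitted.
- **Significant three-way interaction:** compare the slopes by sex from that same model, which respects the stop rule. State the lower precision: with balanced sexes, an assumption, each sex has about 50/2 = 25 children per arm.

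Condition differences at one early and one late puberty value, both fixed in advance, would be a useful optional description.

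The cost is a few sentences of SAP wording and a few more reported contrasts. No new data or models are needed.
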